7. TREATMENT OF PARTICIPANTS

7.1 Treatment Arms

Participants will each receive two IM doses of either LNP-MARVsaRNA (5 μ g) (Group 1), LNP-EBOVsaRNA (4 μ g) (Group 2), LNP-LASSAsaRNA (4 μ g) (Group 3), LNP-MARVsaRNA (5 μ g) plus LNP-EBOVsaRNA (4 μ g) (Group 4) or LNP-MARVsaRNA (5 μ g), plus LNP-EBOVsaRNA (4 μ g) plus LNP-LASSA saRNA (4 μ g) (Group 5) into the deltoid muscle at Week 0 and week 12 (see **Table 3** below). The volume of each injection will be 0.5 mL.

Storage, dispensing, reconstitution and dilution of IMP, the volume for injection and method of administration for each dose level will be described in the EML-Vac Pharmacy Manual.

The saRNA (drug substance) and LNP-saRNA bulk drug product have been manufactured to GMP grade by the Centre for Process Innovation, Darlington, UK and fill finish and labelling has been performed by Nova Laboratories, Wigston, UK. Release of vaccine vials and shipping to the clinical site will be carried out by Nova Laboratories, Wigston, UK.

Table 3: LNP-MARVsaRNA, LNP-EBOVsaRNA and LNP-LASSAsaRNA candidate and dispensing schedule

Study component	Description	Route	Dose	Visit 2 (day/week) Prime	Visit 5(day/week) Boost
				Prime	Boost
Group 1	LNP-MARVsaRNA- 01, plus two buffered saline placebo	IM	5 μg (0.5 mL), plus 2 x 0.5 mL buffered saline	D0/W0	D84/W12
Group 2	LNP-EBOVsaRNA-01, plus two buffered saline placebo	IM	4 μg (0.5 mL), plus 2 x 0.5 mL buffered saline	D0/W0	D84/W12
Group 3	LNP-LASSAsaRNA-01, plus two buffered saline placebo	IM	4 μg (0.5 mL), plus 2 x 0.5 mL buffered saline	D0/W0	D84/W12
Group 4	LNP-MARVsaRNA- 01, LNP-EBOVsaRNA- 01, plus one buffered saline placebo	IM	5 μg (0.5 mL) + 4 μg (0.5 mL) (9 μg per dose), plus 1 x 0.5 mL buffered saline	D0/W0	D84/W12
Group 5	LNP-MARVsaRNA- 01, LNP-EBOVsaRNA-	IM	5 μg (0.5 mL) + 4 (0.5 mL) μg +	D0/W0	D84/W12

01, LNP-LASSA	4 μg (0.5 mL)	
saRNA-01	(13 μg per	
	dose)	

7.1.1 LNP-MARVsaRNA-01, LNP-EBOVsaRNA-01 AND LNP-LASSAsaRNA-01 VACCINES

LNP-MARVsaRNA-01, LNP-EBOVsaRNA-01 and LNP-LASSAsaRNA-01 are aqueous formulations of RNA encapsulated in Lipid Nano Particles (LNP) which are provided at a target concentrations of 10 μ g /mL (LNP-MARVsaRNA-01) or 8 μ g/mL (LNP-EBOVsaRNA-01 and LNP-LASSAsaRNA-01) for IM injection.

LNP-MARVsaRNA-01, LNP-EBOVsaRNA-01 and LNP-LASSAsaRNA-01 vaccines are manufactured by Centre for Process Innovation (CPI) in accordance to GMP standard on behalf of the sponsor, who is also responsible for the product development.

LNP-MARVsaRNA-01, LNP-EBOVsaRNA-01 and LNP-LASSAsaRNA-01 are fill finished by Nova Laboratories and shipped directly to the trial site. Nova Laboratories will supply the IMPs with EML-Vac-specific labels, according to GMP.

The drug products are presented as a white to off-white suspension; in Type I glass vials, with a butyl rubber stopper and aluminium crimp seal. A 0.65 mL fill is provided to allow for 0.5 mL for administration as per instructions in the EML-Vac pharmacy manual.

These vaccine candidates are not classified as a genetically modified organism (GMO).

7.1.2 PLACEBO INJECTIONS

While there is no placebo group planned within this trial, to ensure all participants remain blinded to their group allocation, three injections will be given at each dosing timepoint, irrespective of group. Two placebo doses will be given to participants who are randomised to groups 1-3 and one placebo dose will be given to participants who are randomised to group 4. The placebo dose will consist of 0.5 mL buffered saline.

7.1.3 ADMINISTRATION

Vaccines and placebo should be administered intramuscularly in the deltoid muscle of the upper arm using a 23G 1-inch needle. The participant may choose which arm. All injections should be in the same arm.

To keep the participants blinded, syringes containing the saline and the active drug substance will be covered with a blinding label before entering the room to ensure the participants cannot observe the contents of the syringe.

Participants will be observed for at least 60 minutes after the injection.

7.1.4 STORAGE

The vaccines will be stored in a secure, limited access storage area under the specified storage requirements. The vaccines will be stored according to the Pharmacy Manual and the arrangements will be reviewed at site initiation.

7.1.5 Dose Modifications For Toxicity & Schedule Interruptions

Target visit dates (based on the enrolment date) should be adhered to as far as possible, based on the allowable window (detailed in Table 2). The schedule may be interrupted if a participant has symptoms or signs on the day of scheduled injection, and the investigator considers it best to defer the injection. A temperature over 37.5°C would prevent injection on the day. Clinicians should consult the PI/Medical Delegate if there are any Grade 1 (mild) symptoms or signs listed in **Table 4**. The participant will be asked to return for review within the ideal window period of the scheduled injection. Provided the injection is administered during the window period outlined in the paragraph below for missed visits, this will not be a protocol deviation.

The PI or Medical Delegate should interrupt the vaccine schedule and inform the Chief Investigator within 24 hours using the safety email if there is a confirmed:

Grade 3 (severe) or worse solicited adverse event that has persisted for more than 72 hours regardless
of relationship

or

- other Grade 3 (severe) or worse adverse event that is possibly, probably or definitely related to vaccine or
- serious adverse reaction regardless of grade

The Chief Investigator/Delegate may recommend further investigations or referral to an independent expert to support the clinical management of the participant. Such events are highly likely to result in discontinuation, but a decision to resume will be taken by the PI with the participant, and only with the approval of the independent members of the TSC.

Injections for all participants will be paused pending a review of all safety data by the Trial Steering Committee if two participants out of 20, and the equivalent (10%) thereafter develop persisting Grade 3 (severe) adverse reactions within 7 days of immunisation, or any participant experiences a serious adverse reaction at any time. Approval of an amendment from the competent authorities is required before the trial can be resumed.

If two participants in any Group experience a Grade 3 reaction the trial will be paused and only resumed after approval of a substantial amendment.

Participant visits will continue during a pause. Missed injections will be rescheduled and the remaining trial visits rescheduled/repeated accordingly. There are no known important risks associated with the LNP-MARVsaRNA, LNP-EBOVsaRNA or LNP-LASSAsaRNA vaccine. There is no known antidote. Participants who are overdosed should be closely monitored and provided with medical support per the investigator's judgment.

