9.1 Trial Assessment Schedule

The assessments in clinic and online, samples and volumes to be collected are outlined in: Table 2:

Collection of adverse event data must begin from the time that informed consent if given by the participant.

The maximum blood volume drawn from a participant in the EML-Vac trial, who completes 52 weeks of follow-up in the trial period, is approximately 403 mL. These volumes do not include the blood volume that would be required if additional diagnostic tests are needed, or safety tests have to be repeated. The required volumes per visit together with sample collection and processing guidelines are described in detail in the Laboratory Manual.

The visits in the trial assessment schedule are: a screening visit (Visit 1); an enrolment visit which must take place within 8 weeks of the screening visit and is defined as Week 0 (Visit 2); injection visits at Weeks 0 and 12 (Visits 2 and 5); safety visits at Weeks 1, 4, 13, 14, 16, 24 and 36 (Visits 3, 4, 6, 7, 8, 9 and 10) and a final visit at Week 52 (Visit 11). The visit windows are provided in **Table 2**.

Information on vaccine reactions will be solicited directly from participants for one week following each injection using the participant facing tools in the EDC system. Participants will attend a site visit 1 day after each injection.

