9.4 Procedures for Assessing Safety

Vaccines are associated with a number of well-characterised local, systemic and laboratory reactions referred to as solicited adverse events (**Table 4**). These adverse events will be purposively collected.

Local and systemic assessments will take place on the day of each injection before the injection, and 25-60 minutes after the injection. **Participants should remain in the clinic for at least one hour after each injection.**

Participants will be asked to complete vaccine diary cards on the EDC system to assist collection and grading of local and systemic adverse events that start within 7 days of the injection. They will be advised to contact trial staff if any events are Grade 3 (severe), and these will be flagged in the EDC system for immediate attention with a view to organising an early visit. Information entered will be checked by staff at site 1 day after each injection and at the next visit.

Blood (~10 mL) for routine safety parameters will be collected at all trial visits. If the total bilirubin is elevated, trial staff will request a result for conjugated bilirubin in order to grade the abnormality and determine any action to be taken with respect to further investigation and interruption to the vaccine schedule.

Vital signs (BP, HR, oxygen saturation and oral temperature) will be measured at every trial visit.

Physical examinations of the injection site, and other body systems if indicated, will be performed on the day of each vaccination, and 1 week after. Symptom-directed physical examinations will be performed at all other follow-up visits.

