9.5.2 INNATE IMMUNE RESPONSE

Additional blood samples will be collected to assess serum analysis of the innate response to vaccination. Blood will be taken on the day of each vaccination and 24 hours post each vaccination and processed for serum. These samples will be sent to a central laboratory for processing. Serum will be used to determine soluble markers of innate immune activation such as CXCL10 (IP10) and interferon alpha.

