10.2 Outcome Measures

The outcome measures are:

- Solicited local injection site reactions starting within 7 days of administration of the vaccine: pain, tenderness, erythema, swelling
- Solicited systemic reactions starting within 7 days of administration of the vaccine: pyrexia, fatigue, myalgia, headache, chills, arthralgia
- Unsolicited adverse reactions (ARs) throughout the trial period (including serious ARs)
- Serious Adverse Events
- Unsolicited adverse events throughout the trial period
- The titre of vaccine-induced serum IgG binding antibody responses to the Marburg virus, Ebola virus and Lassa virus surface glycoprotein 2 weeks after the second vaccinations

The exploratory outcome measures are:

- The titre of serum neutralising antibodies 2 weeks after the second vaccination in the Marburg, Ebola and Lassa pseudovirus-based neutralisation assay
- Cell-mediated vaccine-induced immune responses measured by T and B cell ELISpot in participants in the dose escalation and evaluation parts
- Cell-mediated vaccine-induced immune responses measured by flow cytometry and intracellular cytokine staining in participants in the dose escalation and evaluation parts
- Serum markers of innate immune response

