10.3.2 IMMUNOGENICITY

A total of 40 participants will be included in the randomised evaluation of immunogenicity, 8 participants per group. The primary analysis will compare binding antibody responses to Ebola virus, Lassa virus and Marburg virus glycoproteins at 14 weeks (2 weeks after the booster at 12 weeks). It is difficult to give an estimate of the power of group comparisons using quantitative antibody titre outcomes at this stage as this is dependent on the number of responders, and the large number of experimental parameters in this experimental trial. The main objective of groups 1-5 is to assess whether overall immune responses to individual Ebola, Lassa and Marburg LNP saRNA vaccines given alone are similar to those administered in combination. No formal hypothesis testing will be performed for immunogenicity endpoints; all comparisons will be descriptive. Ideally, binding and neutralisation antibody should be observed in 100% of participants. With a sample size of 8 participants per group, the lower 5% CI for the response rate is 68-100% if there are no non-responders, and 41-93% if there are two non-responders in any group. The number of 'responders' in each assay will be presented for each timepoint and group as a proportion with a 95% confidence interval. A 'responder' will be defined as a participant in whom a response was detected in two weeks after the final vaccination immunogenicity sample. A positive result will be defined relative to a pre-defined cut-off threshold value and assays will be validated using predefined thresholds based on the responses to positive and negative control stimuli. More information on the assay and definition of positive results will be supplied

in the SAP. Titres of antigen specific antibodies will be described by timepoint and group and compared using rank tests, where appropriate.

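### Visit dates are anchored to enrolment, but the main titre outcome is timed from the boost, so the V7 sample can fall outside 14 ± 2 days after the second injection

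*Protocol*

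**What the plan says.** Section 7.1.5 gives the anchor for the schedule: "Target visit dates (based on the enrolment date) should be adhered to as far as possible, based on the allowable window". Section 9.1 defines enrolment as Week 0 (Visit 2), the day of the first injection. Table 2 then gives these days and windows:

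- V5 (second injection): day 84, −4 to +7
- V5a: day 85, no window
- V6: day 91, 0 to +2
- V7: day 98, −2 to +2
- V8: day 112, −4 to +4

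Other sections time the same contacts from the injection. The antibody outcome in section 10.2 is the titre to the Marburg, Ebola and "Lassa virus surface glycoprotein 2 weeks after the second vaccinations". Section 10.3.2 places the primary immunogenicity comparison of responses to the three "glycoproteins at 14 weeks (2 weeks after the booster at 12 weeks"), and defines a responder from the sample taken two weeks after the final vaccination. Section 9.1 says "Participants will attend a site visit 1 day after each injection", section 9.4 says of the diary "Information entered will be checked by staff at site 1 day after each injection and at the next visit", and section 9.5.2 says of the innate markers "Blood will be taken on the day of each vaccination and 24 hours post each vaccination and processed for serum".

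Two further sentences in section 7.1.5 deal with late injections. For a deferred injection: "Provided the injection is administered during the window period outlined in the paragraph below for missed visits, this will not be a protocol deviation". After a sentence on pauses: "Missed injections will be rescheduled and the remaining trial visits rescheduled/repeated accordingly".

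**The concern.** The protocol uses two clocks for the post-boost visits. The one explicit anchor statement runs from enrolment; the outcome definitions run from the second injection. The two agree only when the boost is given on day 84, yet Table 2 allows it on any of 12 days, with more room on the late side (+7) than on the early side (−4).

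V7 carries the serum sample for the IgG titre 2 weeks after the boost, and that sample also decides who is a responder. If the boost slips within its own window and V7 stays on its enrolment date, the sample is taken at a different point of the post-boost response from the one the outcome names. With 8 participants per group, one mistimed participant is 1/8 = 12.5% of a group. An analysis plan could flag or exclude such a sample but could not redraw it.

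**Working it through.** **Inputs.** Table 2 days and windows as listed above; the enrolment anchor from section 7.1.5; the interval of 2 weeks (14 days) from sections 10.2 and 10.3.2. The tolerance of ±2 days is V7's own window in Table 2; the outcome definition itself states no tolerance.

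**The plan's own figure.** V7 minus V5 at nominal days: 98 − 84 = 14 days. This reproduces the equation of week 14 with 2 weeks after the booster. V5a minus V5: 85 − 84 = 1 day. Both hold at nominal days.

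**V7 includes the serum draw.** The serum row of Table 2 is hard to read at V7, but the visit total is 76 mL, and 76 − 10 (safety bloods) − 60 (cellular assays) = 6 mL, the volume of the serum sample.

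**Permitted days, counted from enrolment.**

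- V5: 84 − 4 = 80 to 84 + 7 = 91, which is 12 days
- V5a: 85 only
- V7: 98 − 2 = 96 to 98 + 2 = 100

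**Days after a boost on day b.** V7 falls at (96 − b) to (100 − b); V5a falls at 85 − b.

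| Boost day b | V7, days after boost | Overlaps 12–16? | V5a, days after boost |
|---|---|---|---|
| 80 | 16–20 | yes (16 only) | +5 |
| 84 | 12–16 | yes (all) | +1 |
| 85 | 11–15 | yes | 0 |
| 88 | 8–12 | yes (12 only) | −3 |
| 89 | 7–11 | no | −4 |
| 90 | 6–10 | no | −5 |
| 91 | 5–9 | no | −6 |

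**Extremes for V7.** Minimum 96 − 91 = 5 days; maximum 100 − 80 = 20 days.

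**When V7 cannot be met.** An overlap with 12–16 days needs 100 − b ≥ 12, so b ≤ 88, and 96 − b ≤ 16, so b ≥ 80. Boost days 80 to 88 (9 of 12) leave at least one suitable V7 date; days 89, 90 and 91 (3 of 12) leave none. These are counts of calendar days, not probabilities.

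**V5a.** With a fixed day 85, the 1-day interval required by sections 9.1, 9.4 and 9.5.2 holds only for b = 84.

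**V8.** It falls at (108 − b) to (116 − b). This overlaps 24–32 days for every permitted b (28–36 for b = 80; 17–25 for b = 91), so V8 can always be met.

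**With the boost as anchor and the same windows.** V5a at 1 day, V6 at 7 to 9 days, V7 at 12 to 16 days, V8 at 24 to 32 days.

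**The case against.** The strongest reply is that the protocol, read as a whole, makes its intention plain. Every definition of the titre outcome runs from the injection, and section 10.3.2 explains its week-14 timepoint at once as 2 weeks after the booster. Section 7.1.5 sets target dates and asks for adherence only as far as possible. Its rescheduling sentence shows that visits are meant to follow the injection. The 5- and 20-day figures need opposite ends of two windows to coincide. Section 9.3.3 has the injection time recorded, so the actual interval should be recoverable, and the analysis plan, which is not at hand, may set rules for samples outside the interval. Comparisons are descriptive in any case.

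Much of this stands, and it limits the point. It does not remove it. The rescheduling sentence speaks of missed injections, directly after a sentence on pauses. A boost on day 90 is inside its Table 2 window, so it is not clearly missed. The window for missed visits cited for deferred injections is given no number of days, so it does not settle the matter either. No sentence says that the V7 window runs from the actual boost.

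Three stronger readings are tempting and are not supported:

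- A reader might infer that the protocol permits a 24-hour visit or innate-marker sample before the boost. Sections 9.1, 9.4 and 9.5.2 require these 1 day or 24 hours after each injection, and section 4.1.1 requires the same visit for sentinels. This is an internal contradiction with the fixed day 85, which sites would probably resolve correctly.
- A reader might infer from the V6 dates that post-boost diary data would be lost. Section 9.1 has reactions solicited for a week after each injection, and section 9.4 has the diary completed electronically, with severe events flagged for immediate attention.
- A reader might infer bias between groups. Nothing in the protocol suggests that boost timing would differ by group.

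**Conclusion.** The point holds for V7. The stated anchor can mistime the only non-exploratory immunogenicity outcome and the sample that defines a responder: 5 to 20 days after the boost at the extremes, with no compliant date within 14 ± 2 days when the boost falls on days 89 to 91. For V5a there is an inconsistency of wording and little practical risk.

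This rests on two assumptions: that section 7.1.5 is followed as written for a boost given inside its own window, and that V7's ±2 days is a fair tolerance for 2 weeks. The frequency of boosts on days 89 to 91 cannot be derived, so neither can the expected number of mistimed samples. Severity is minor to moderate. The correction is still worth making, because it is cheap and a mistimed sample cannot be recovered at analysis.

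**What to change.** In section 7.1.5 and in a footnote to Table 2, time V5a, V6, V7 and V8 from the actual date of the second injection, at +1, +7, +14 and +28 days, with the existing windows unchanged (none; 0 to +2; −2 to +2; −4 to +4). V7 then falls 12 to 16 days after the boost. In section 10.3.2, replace the week-14 timepoint with 14 days (±2) after the second injection.

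The cost is a few sentences and one footnote, with no added visit, sample or participant. The downside is that post-boost visits move with the boost: by at most 7 days later (91 − 84) or 4 days earlier (84 − 80) for a boost inside its window. The latest V8 would be day 91 + 28 + 4 = 123, well before the earliest V9 at day 168 − 7 = 161, so later visits can stay on their present dates.

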4. STUDY OBJECTIVES

EML-Vac is a trial that is looking at new RNA vaccines against the Marburg, Ebola and Lassa viruses which are the major causes of viral haemorrhagic fever. The aim of the trial is to assess the safety of these vaccines alone and in combination, since this will be the first time that these have been used in humans. As this is a first-in-human trial, accrual will be limited to healthy adults between 18-50 years. Safety data will be assessed as an event rate and confidence interval with clear thresholds for pausing vaccinations in an individual and the trial (see Section 7.1.5). Provided the threshold for pausing vaccines in the trial is not crossed, immunogenicity will be determined by the quantity of binding antibodies 2 and 4 weeks after the last injection. As placebo does not inform the analysis for either of these endpoints, there will be no allocation to a placebo group. However, placebo doses of buffered saline will be administered I.M to ensure the participants remain blinded as to their group randomisation.

This trial is NOT looking at whether the vaccines are effective in terms of protection. It is just assessing whether and how well the immune system responds to the vaccine.

As exploratory endpoints, we will assess participants' neutralising antibody titres, B cell responses, and T cell responses to explore any associations with the induction of neutralising titres. We will also assess serum markers of innate response to both immunisations. Peripheral blood mononuclear cells (PBMCs) from participants will be processed for the isolation of antigen-specific B cells to isolate neutralising monoclonal antibodies to enhance understanding of targeted epitopes, with priority given to those showing higher serum neutralising antibody titres.

Objectives

- ➤ To evaluate the safety and immunogenicity of two immunisations with LNP-MARVsaRNA-01 administered IM 12 weeks apart at a 5 µg dose in 8 participants age 18-50 years.
- To evaluate the safety and immunogenicity of two immunisations with LNP-EBOVsaRNA-01 administered IM 12 weeks apart at one dose levels 4 μg in 8 participants age 18-50 years.
- To evaluate the safety and immunogenicity of two immunisations with LNP-LASSAsaRNA-01 administered IM 12 weeks apart at one dose levels 4 μg in 8 participants age 18-50 years.

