- 9. At 48 (-/+5) hours post-vaccination the team will call the fourth participant and go through their diaries. If the reactions are Grade 1-2, or transient Grade 3 that resolve within 24 hours, the fifth participant may receive 5 μ g of LNP-MARVsaRNA plus 4 μ g of LNP-EBOVsaRNA plus 4 μ g of LNP-LASSAsaRNA

- 10. At 1 day post immunisation, the fifth participant will attend the trial site to review AEs and donate blood to measure innate immune responses.
- 11. At 48 (–/+5) hours post-vaccination the team will call the fifth participant and go through their diaries. If the reactions are Grade 1-2, or transient Grade 3 that resolve within 24 hours, the dose evaluation cohort of remaining 35 participants may start to be enrolled and randomised into one of the 5 groups to receive their first immunisation.
- 12. Sentinel participants will be evaluated again as above after receiving their second dose. If the reactions are Grade 1-2, or transient Grade 3 that resolve within 24 hours, the cohort of remaining 35 participants may receive their second dose

The steps above describe the fastest plan to enrol into the 5 groups and is justified based on previous experience with this self-amplifying RNA platform. However, if there are persistent Grade 3 reactions observed in any of the sentinels, the team will invite the affected participant to attend the trial site in order to evaluate these and will proceed to vaccinate a second sentinel within the same group. The group will not be changed until at least 1 participant has provided acceptable safety data to at least 48 (–/+5) hours post-vaccination. If 2 or more of the participants at any dose level in this part of the trial have persistent Grade 3 (or worse) reactions, or if 1 or more has a serious adverse reaction, the dose will not be expanded, and the trial stopping rules described below (7.1.5) will be triggered.

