11. MONITORING

The trial will be overseen by a Trial Steering Committee (TSC), which will include membership independent of the Trial Management Group (TMG). The reason for this is the need for real-time assessment of the safety data. The TSC will be informed by the Chief Investigator when the first participant receives the first injection of 5 μg, and a report of 7-day reactogenicity will be provided when the first 4 individuals have completed their Week 1 visit (see Section 4.1.1). The TSC will receive weekly progress reports. Weekly reports will continue whilst day 7 data are accumulating; after which point the frequency will be determined by the TSC (in accordance with the TSC Charter). Any adverse reactions that lead to interruption in the schedule for an individual or plan for enrolments described in Section 7.1.4 will be immediately reported to the TSC. The site will be requested to notify the Chief Investigator within 24 hours of any adverse reaction that is a cause for concern as described in Section 8. These reports will be shared with the Trial Steering Committee immediately. If there are 2 out of 8 participants (25% thereafter) who experience similarly severe adverse reactions, vaccinations will be paused in all individuals and the competent authority informed. The TSC will be asked to review the accumulating safety data from all participants and make a recommendation about resuming vaccinations.

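### Section 11 states an all-participant pause at 2 of 8, then 25%, while the governing rule in 7.1.5 says 2 of 20, then 10%

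*Protocol*

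**What the plan says.** **Where the rules are meant to be.** Section 4 refers to 7.1.5 for the thresholds that pause dosing in an individual or in the trial. Section 4.1.1 says that, if sentinel reactions are bad enough, "the trial stopping rules described below (7.1.5) will be triggered".

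**Protocol 7.1.5.** Injections stop for everyone, pending a Trial Steering Committee (TSC) review of the safety data, on any of three triggers:
- "if two participants out of 20, and the equivalent (10%) thereafter develop persisting Grade 3 (severe) adverse reactions within 7 days of immunisation";
- one serious adverse reaction at any time;
- a Grade 3 reaction in two participants of any one group.

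The first two require an amendment approved by the competent authorities before the trial resumes. The group trigger requires approval of a substantial amendment.

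**Protocol Section 11.** After asking the site to report promptly any reaction of concern as described in Section 8, the text says: "If there are 2 out of 8 participants (25% thereafter) who experience similarly severe adverse reactions, vaccinations will be paused in all individuals". The competent authority is then informed, and the TSC is to review the data and "make a recommendation about resuming vaccinations". Adverse reactions that interrupt the plan "described in Section 7.1.4 will be immediately reported to the TSC".

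**Protocol 7.1.4** deals with vaccine storage. The line after Table 6 in 8.2.4 also sends the reader to 7.1.4 when injections are interrupted.

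**The concern.** Both texts describe a pause for all participants, but with different counts, percentages and event descriptions. A first-in-human trial needs one boundary for stopping all dosing.

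Section 11 is the text that describes what the TSC does. Under 13.3 the TSC takes the final decision on continuing the trial, and under 13.4 there is no separate data monitoring committee. A TSC member who works from Section 11 sees the looser percentage and no mention of an amendment, and the cross-reference leads to storage. If the two percentage rules count the same events, that reader could let dosing go on past the point at which 7.1.5 stops it.

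**Working it through.** **Inputs.** 7.1.5: 2 of 20, then 10%. Section 11: 2 of 8, then 25%. Sample size: 40, in five groups of 8 (Table 1).

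**Each rule against itself.** 2/20 = 10% and 2/8 = 25%, so each is internally consistent. The conflict is between them.

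**Thresholds if both count the same events.** I assume a percentage is met when the count reaches it, with a minimum of two cases. The trigger at n dosed is then max(2, ⌈0.10n⌉) under the 7.1.5 percentage rule and max(2, ⌈0.25n⌉) under Section 11.

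| Dosed | 7.1.5 percentage rule | Section 11 |
|---|---|---|
| 8 | 2 | 2 |
| 20 | 2 | 5 |
| 30 | 3 | 8 |
| 40 | 4 | 10 |

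**Effect of the 7.1.5 group rule.** Two Grade 3 cases in one group pause the trial whatever the percentage. The percentage conflict decides alone only when no group has more than one case, so with at most five cases. The counts at which 7.1.5 pauses on its percentage rule alone and Section 11 does not are therefore 2–4 at 20 dosed, 3–5 at 30 and 4–5 at 40.

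**When the 25% figure can act first.** At 21 dosed, 0.25 × 21 = 5.25, which rounds up to 6. Six cases in five groups put at least two in one group. From 21 dosed, if Section 11 counts Grade 3 reactions, the group rule is therefore met no later than the 25% rule. At 9 to 20 dosed the 25% threshold is only 3 to 5 cases. These could be transient Grade 3 reactions in different groups, meeting neither the group rule nor the persisting-reaction rule. In that range Section 11 could act first if it counts such reactions.

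**Illustration of size.** The documents give no rate of persisting Grade 3 reactions for these vaccines. As an assumption, take the 2/24 = 8.3% in Table 5 (any systemic Grade 3 at 5 µg of the earlier vaccine, not only persisting), with a range of 5% to 15%.
- Checking after each participant up to 40 (100,000 simulated trials), the chance of ever meeting the 10% rule is about 0.62 (range 0.32–0.93). For the 25% rule it is 0.16 (0.06–0.44).
- For the group rule alone, P(at least 2 of 8) = 0.139 at 8.3%, so the chance in at least one of five groups is 1 − (1 − 0.139)^5 = 0.53 (range 0.26–0.88).

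The contradiction does not depend on these rates. They show that the two percentages behave very differently, and that the group rule would often stop the trial.

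**Can Section 11 be read as a per-group rule?** Two of 8 matches the group size and the 7.1.5 group count. But Section 11 names no group, and a percentage to apply beyond 8 participants has no use in a group of 8. The 7.1.5 group rule also carries no percentage.

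**The case against.** The strongest reply is that the two rules may count different things. In Section 11 the comparison with similarly severe reactions looks back to reactions of concern under Section 8. Section 8.1.4 lists solicited Grade 3 events lasting more than 72 hours, confirmed Grade 3 laboratory events, and any event that interrupts dosing. Some persistence is therefore built in, and the set is visibly not that of 7.1.5. This stands: the same-events comparison is conditional, and it cannot be said that Section 11 always pauses later. It does not remove the problem, because the text never says that the two rules are separate or how they relate.

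A reader might infer that Section 11 lets dosing resume on TSC advice alone, or cancels the single-serious-reaction trigger. The documents do not support this. 7.1.5 also provides for TSC review and then adds the amendment. Section 11 does not say that an amendment is unnecessary, and the serious-reaction trigger still stands in 7.1.5. These are omissions.

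A reader might also see a conflict between 4.1.1 and 7.1.5. Section 4.1.1 invokes the stopping rules "If 2 or more of the participants at any dose level in this part of the trial have persistent Grade 3 (or worse) reactions"; after one such case the team "will proceed to vaccinate a second sentinel within the same group". A transient Grade 3 reaction in that second sentinel would permit progression under 4.1.1 and pause the trial under the group rule. But 4.1.1 only permits the next dosing, which does not override an unconditional pause. Its notion of persistence is also readable from the contrast with Grade 3 reactions that resolve within 24 hours.

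**Conclusion.** The point holds for the threshold. Section 11 states an all-participant pause percentage that differs from the one in the section the protocol itself names as governing, and no per-group reading reconciles them. On the assumption that both percentages apply to the same events, the triggers are 2 against 5 at 20 dosed, 3 against 8 at 30 and 4 against 10 at 40. The group rule narrows the practical gap. From 21 dosed it closes it on the late side, provided that Section 11 counts Grade 3 reactions.

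It would go too far to say that the 25% figure can never be the first trigger: that is shown only from 21 dosed. The missing amendment requirement is an omission that 7.1.5 still covers. The wrong cross-reference is clerical on its own, but here it keeps the reader of Section 11 from reaching the governing rule. Because the error lies in a stated safety threshold and costs little to repair, it should be corrected.

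**What to change.** - In Section 11, delete the 2-of-8 and 25% threshold and the restart text. Replace them with a reference to the pause and restart rules in 7.1.5.
- Change the references to 7.1.4 in Section 11 and after Table 6 in 8.2.4 to 7.1.5.
- Optionally, state in the trial-level rule of 7.1.5 that a persisting reaction is one lasting more than 72 hours, as in the individual-participant rule of 7.1.5 and in 8.1.4.

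No new reporting duty and no change to the sentinel steps is needed. The cost is a wording amendment with no added participants, visits or procedures. Because it touches the pausing rules, and version 2.0 was itself updated in response to the regulator, it may need regulatory approval.
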